11.3 Early Termination of Subjects from the Study

Subjects are free to withdraw from the study at any time for any reason.

In addition, subjects may be withdrawn from the study by the PI or designee for the following reasons:

- AEs.
- Difficulties in blood collection.
- Positive pregnancy test.
- Positive urine drug and alcohol test.

A subject may be withdrawn by the PI, designee, or the Sponsor if either considers enrollment of the subject into the study is inappropriate, the study plan is violated, or for administrative and/or other safety reasons. Prompt notification to the Sponsor of withdrawal of any subject should be provided.

Subjects who withdraw from the study will undergo early termination from the study procedures as outlined in the Study Events Flow Chart ([Section 6](#)).

11.4 Study Restrictions

11.4.1 Prohibitions and Concomitant Medication

Consumption of foods and beverages containing the following substances will be prohibited as indicated:

- Xanthines/Caffeine: 24 hours prior to dosing and through EOT or ET (small amounts of caffeine derived from normal foodstuffs e.g., 250 mL/8 oz./1 cup decaffeinated coffee or other decaffeinated beverage, per day, with the exception of espresso; 45 g/1.5 oz. chocolate bar, per day, would not be considered a deviation to this restriction);
- Alcohol: 48 hours prior to dosing and through EOT or ET;
- Grapefruit/Seville orange and their juices: 14 days prior to dosing and through EOT or ET;

- Other Fruit Juice: 72 hours prior to dosing and through EOT or ET;

Participation in any other investigational study drug trial in which receipt of any investigational drug occurs within 5 half-lives (if known) or 30 days, whichever is longer, prior to dose administration (Day 1) is prohibited.

Any prescription or over-the-counter medications (including herbal products, natural or vitamin supplements) will be prohibited for at least 14 days prior to dosing through EOT or ET, unless allowed by the PI (or designee), with agreement from the Sponsor, as described below.

Any prescription or non-prescription medications that are inhibitors or inducers of CYP3A4 and CYP3A5 or of P-gp will be prohibited for at least 28 days prior to dosing through EOT or ET.

Any proton pump inhibitors, H2-receptor antagonists or antacids will be prohibited for 14 days prior to dosing and through EOT or ET.

Any drugs that prolong the QT/QTc interval will be prohibited for 14 days prior to dosing and through EOT or ET.

From Day -1 through EOT or ET, any concurrent medication including both prescription and non-prescription drugs must be discussed with the PI (or designee), and/or Sponsor prior to use, unless appropriate medical care necessitates that therapy should begin before the PI (or designee) and/or Sponsor can be consulted. HRT is not permitted. Following study drug administration on Day 1, acetaminophen (up to 2 g per 24 hours) may be administered at the discretion of the PI (or designee).

If deviations occur, the PI or designee in consultation with the Sponsor if needed will decide on a case-by-case basis whether the subject may continue participation in the study.

All medications taken (including vitamins and supplements) by subjects during the course of the study will be recorded.

11.4.2 Meals

Subjects will fast overnight for at least 10 hours prior to study drug administration and will continue to fast for at least 4 hours postdose.

When confined, standard meals and snacks will be provided at appropriate times, except when they are required to fast. When confined in the CRU, subjects will be required to fast from all food and drink except water between meals and snacks. The Day 2 scheduled laboratory assessment must be obtained under fasting conditions (i.e., prior to the scheduled standard breakfast).

Each meal and/or snacks served at the CRU will be standardized and will be similar in caloric content and composition and will be taken at approximately the same time in each period.

11.4.3 Activity

Subjects will remain ambulatory or seated upright for the first 4 hours postdose, except when they are supine or semi-reclined for study procedures.

However, should AEs occur at any time during this period, subjects may be placed in an appropriate position or will be permitted to lie down on their right side.

Subjects will be instructed to refrain from strenuous physical activity which could cause muscle aches or injury, including contact sports at any time from 5 days prior to Check-in (Day -1) until EOT or ET.

Subjects will not be permitted to smoke or ingest tobacco or nicotine containing products from 3 months prior to Screening through the EOT or ET.

12 TREATMENTS

12.1 Treatments Administered

LOXO-292 will be supplied as 80 mg capsules.

Subjects in each cohort will receive a single oral dose of LOXO-292 on Day 1 preceded by an overnight fast of at least 10 hours and followed by a fast from food (not including water) for at least 4 hour postdose.

Planned dose levels will be as follows:

Cohort 1:	320 mg LOXO-292 (4 x 80 mg capsules) on Day 1
Cohort 2:	≤ 640 mg LOXO-292 (≤ 8 x 80 mg capsules) on Day 1
Cohort 3: (Optional)	≤ 720 mg (≤ 9 x 80 mg capsules) LOXO-292 on Day 1

Additional cohorts (6 subjects per cohort) may be enrolled if it is deemed appropriate to repeat any dose level, or to add an interim dose levels or levels (lower than 720 mg), as determined by the Sponsor in consultation with the PI, depending on the safety and tolerability results from the prior cohort(s). Dosing will not exceed 720 mg in any subject.

All study drugs will be administered orally after an overnight fast with approximately 240 mL of water. Additional water in increments of 50 mL up to a maximum of 100 mL may be administered if needed by the subject.

Subjects will be instructed not to crush, split, or chew LOXO-292 capsules.

The pharmacy at the CRU will provide each dose in individual unit dose containers for each subject.

The exact clock time of dosing will be recorded.

12.2 Dose Modification

The dose and administration of the study drug to any subject may not be modified unless as otherwise decided in accordance to the dose escalation criteria. If necessary a subject must be discontinued for the reasons described in [Section 11.3](#).

12.3 Method of Treatment Assignment

Each subject will be assigned a unique identification number upon screening. Subjects who complete the study screening assessments and meet all the eligibility criteria will be assigned a unique randomization identification number at the time of the dosing, different from the screening number.

All subjects will receive LOXO-292.

Subjects may be replaced at the discretion of the Sponsor.

If replacement subjects are used, the replacement subject number will be 100 more than the original (e.g., Subject No. 101 will replace Subject No. 001).

12.4 Blinding

This is an open-label study.

12.4.1 Dose Escalation Criteria and Stopping Rules

The decision to proceed to the next higher dose administration will be made following the review of all pertinent safety/tolerability data (e.g., physical examinations, ECGs, vital signs, clinical laboratory tests, and AEs) from all subjects through a minimum of 48 hours (Day 3) postdose for Cohort 1 and through a minimum of 120 hours postdose (Day 5) for Cohort 2. Dose escalation to the next dose level (i.e., next cohort) will not take place until the PI and the Sponsor have determined that adequate safety and tolerability from the previous, lower dose, cohort has been demonstrated to permit proceeding to the next cohort.

Together they will make one of the following determinations:

1. To continue with the study as planned.
2. To continue with the study and add additional safety evaluations to subsequent cohorts.
3. In the event of the following occurrence:

One (1) or more subject(s) at a given dose level experiences a drug related CTCAE grade ≥ 3 toxicity, which is deemed clinically significant by the PI or designee with agreement from the Sponsor, a decision will be made as follows:

- Continue with the study by repeating the current dose;
- Adjust to an intermediate dose between the current dose and the next planned dose;
- Adjust to an intermediate dose between the current dose and the previous lower dose;
- Dose administration may be permitted to continue as deemed by PI, in agreement with the Sponsor, where the safety parameter assessed does not pose a subject safety risk based on safety knowledge from prior LOXO-292 studies.

4. In the event of the following occurrence:

Two (2) or more subjects in a dose level experience a drug related CTCAE grade ≥ 3 toxicity, which are deemed clinically significant by the PI or designee with agreement from the Sponsor, a decision will be made as follows:

- Dose administration may be permitted to continue as planned if deemed acceptable by PI, in agreement with the Sponsor, where the safety parameter assessed does not pose a subject safety risk based on safety knowledge from prior LOXO-292 studies;
- Evaluate an alternative dose level;
- The study may be terminated with no additional dose administration to any subjects.

5. One (1) or more subject(s) in a dose level has a drug related SAE, a decision will be made as follows:

- Evaluate an alternative dose level;
- The study will be terminated with no additional dose administration to any subjects in any cohort.

Bioanalytical data may be used, if available, to guide dose-escalation decisions or for selection of an alternate dose for evaluation, and/or to confirm the sampling schedule.

A sufficient period of time will be allowed between Day 3 of Cohort 1 and the dose of the next cohort and between Day 5 of Cohort 2 and the dose of the next cohort in order for the PI and the Sponsor to adequately review the safety and tolerability data from the prior cohort.

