	
A sufficient period of time will be allowed between Day 3 of Cohort 1 and the dose of the next cohort and between Day 5 of Cohort 2 and the dose of the next cohort in order for the PI and the Sponsor to adequately review the safety and tolerability data from the prior cohort.

Key Assessments:	
Safety: All safety assessments, including AEs and SAEs, vital sign measurements, clinical laboratory results, physical examination results, concomitant medications, and ECG interpretations, will be tabulated and summarized where possible, using descriptive methodology by treatment and time point.
 
Pharmacokinetics: The following PK parameters will be calculated for LOXO-292 in plasma, as appropriate: AUC_{0-t}, AUC₀₋₂₄, AUC_{0-inf}, AUC%extrap, CL/F, Cmax, Tmax, Kel, t_{1/2}, and Vz/F. Future analysis in plasma for metabolite(s) formation may be conducted.

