- d: To be performed at EOT or at ET. EOT is defined as when the subject is released from the CRU following completion of all assessments through Day 8. ET is defined as when the subject is released from the CRU if the subject terminates the study early. Vital signs, ECGs, clinical safety laboratory results for serum chemistry, hematology, coagulation, and urinalysis, and AEs are to be available for review by the PI or designee prior to subject release from the CRU at EOT or ET.
- e: To be performed 7 days (\pm 2 days) following EOT or ET. End of Study (EOS) is defined as when the CRU contacts the subject by phone call 7 days (\pm 2 days) after EOT or ET to determine if any SAE or study drug related AE has occurred since EOT or ET. All subjects who received LOXO-292 (including subjects who terminate the study early) will be contacted.
- f: Symptom-driven physical examination(s) may be performed at other times, at the PI's or designee's discretion. Scheduled abbreviated physical examinations will include, at a minimum, examination of respiratory, cardiovascular, and gastrointestinal systems, with the option for further examination of additional systems as necessary based on reported symptoms/AEs.
- g: Subjects are to be supine for at least 10 minutes prior to ECG assessment. ECGs will be obtained prior to and as close as possible to the scheduled blood draws if scheduled at the same time.
- h: Vital signs (HR and BP) will be obtained at Screening, C-I (Day -1), predose, and at 2 hours (\pm 10 minutes) and 4 hours (\pm 10 minutes) postdose on Day 1, and once daily through EOT (or ET). Vital sign measurements should be carried out prior to and as close as possible to having blood drawn. BP and HR will be measured using the same arm for each reading. Subjects are to be supine for at least 5 minutes prior to vital signs assessments.
- i: To be performed within 2 hours prior to dosing on Day 1.
- j: Samples for serum chemistry will be obtained following a fast of at least 12 hours at Screening and at C-I (Day -1); at other scheduled times, serum chemistry tests will be performed after at least an 8-hour fast. However, in case of dropouts or rechecks, subjects may not have fasted for 12 or 8 hours prior to the time that the serum chemistry sample is taken. The Day 2 scheduled laboratory assessment must be obtained under fasting conditions.

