- k: AEs and SAEs will be recorded beginning at informed consent. AEs will be recorded throughout the study (i.e., from signing of the ICF until EOS or ET if the subject discontinues from the study and does not complete a follow up call), either as subject medical history (if the event is reported as beginning prior to signing of the ICF or if the event occurs prior to study drug administration on Day 1 and is assessed as not related to study procedures by the PI [or designee]) or as AEs (if the event occurs after signing of the ICF but prior to study drug administration on Day 1 and is assessed as related to study procedures by the PI [or designee], or if the event occurs after study

drug administration on Day 1 through EOT or ET regardless of relationship to study drug). From EOT or ET through EOS only AEs assessed as related to study drug by the PI (or designee) are to be reported. All SAEs that develop from the time of ICF signing until EOS (or ET, if the subject discontinues from the study and does not complete a follow up call) are to be reported.

- l: The sampling windows for PK blood samples will be as follows: within 30 minutes prior to dosing for the predose sample time point; \pm 5 minutes for sampling time points within the first 12 hours; \pm 30 minutes for sampling time points > 12 hours \leq 36 hours; and \pm 60 minutes for the sampling time points from ≥ 48 to ≤ 168 hours.
- m: To be performed prior to dosing.
- n: Subjects will be confined to the CRU until the completion of 168-hour blood draw and EOT procedures or until completion of ET procedures.

Abbreviations: ♀ = Females, AE = Adverse events, BP = Blood pressure, C-I = Check-in, Chem = Chemistry, Coag = coagulation, ConMeds = Concomitant medication, CRU = Clinical research unit, ECG = Electrocardiogram, EOS = End of Study, EOT = End of Treatment, ET = Early termination, FSH = Follicle-stimulating hormone, FU = Follow up, Hem = Hematology, HIV = Human immunodeficiency virus, HR = Heart rate, ICF = Informed consent form, PI = Principal Investigator, PMP = Postmenopausal, Preg = Pregnancy, PK = Pharmacokinetic, SAE = Serious adverse event, Scr = Screening, T = Temperature, UA = Urinalysis.

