10 STUDY DESIGN

10.1 Overall Study Design and Plan

This is a Phase I, safety, tolerability, and PK SAD study.

Screening of subjects will occur within 28 days prior to dosing.

The study is planned to enrol up to 18 healthy, adult male and female (of non-childbearing potential only) subjects. Every attempt will be made to enrol at least 1 female in each cohort.

Up to 3 cohorts are planned for evaluation. In each cohort, 6 healthy adult subjects are planned for evaluation. Subjects will participate in only one cohort. In each cohort, subjects will receive a single oral dose of LOXO-292 on Day 1. Cohort 2 and possibly Cohort 3 will include a sentinel group of 2 subjects who will be dosed at least 48 hours before the remaining 4 subjects. Blood samples will be collected for the PK assessment of LOXO-292 in plasma for 168 hours postdose.

Safety and tolerability will be assessed through EOT or ET by monitoring AEs, performing physical examinations, and clinical laboratory tests, measuring vital signs, and recording ECGs.

Dose escalation to a higher dose level (i.e., next cohort) will not take place until the PI and the Sponsor have reviewed all pertinent safety/tolerability data (e.g., physical examinations, ECGs, vital signs, clinical laboratory tests, and AEs) through a minimum of 48 hours (Day 3) postdose for Cohort 1 and through a minimum of 120 hours postdose (Day 5) for Cohort 2 and have determined that adequate safety and tolerability from the previous, lower dose, cohort has been demonstrated to permit proceeding to the next cohort. Bioanalytical data, if available, may be used to guide the dose-escalation decision.

Timing of all study procedures are indicated in the Study Events Flow Chart ([Section 6](#)).

Subjects may be replaced at the discretion of the Sponsor.

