13.2.2 Vital Signs

Single measurements of body temperature, blood pressure, and heart rate, will be measured as outlined in the Study Events Flow Chart ([Section 6](#)). Additional vital signs may be taken at any other times, if deemed necessary.

Vital sign measurements should be carried out prior to and as close as possible to having blood drawn. Blood pressure and heart rate will be measured using the same arm for each reading. Blood pressure, heart rate, and temperature measurements will be performed with subjects in a supine position (at least 5 minutes),

Blood pressure and heart rate will be measured at Screening, at Check-in (Day -1), at predose and at 2 hours (\pm 10 minutes) and 4 hours (\pm 10 minutes) postdose on Day 1, and once daily on each Study Day through EOT or ET (CRU discharge).

Body temperature will be measured at Screening, at Check-in (Day -1), at predose, and at the EOT or ET (CRU discharge).

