13.2.3 ECG Monitoring

Single 12-lead ECGs will be performed as outlined in the Study Events Flow Chart ([Section 6](#)). Additional ECGs may be taken at any other times, if deemed necessary by the PI or designee.

ECGs will be performed with subjects in a supine position (at least 10 minutes). All ECG tracings will be reviewed by the PI or designee.

ECGs will be measured at Screening, at Check-in (Day -1), Days 2 and 5 postdose, and at the EOT or ET (CRU discharge). ECGs will be obtained prior to and as close as possible to the scheduled blood draws if scheduled at the same time.

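### The Cohort 2 safety-review minimum is given as 120 hours and as Day 5, but on the protocol's own calendar Day 5 is 96 hours and 120 hours is Day 6

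*Protocol*

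**What the plan says.** Section 12.4.1 sets the minimum follow-up that the PI and the Sponsor must review, for all subjects, before the next dose level. For Cohort 1 it is "through a minimum of 48 hours (Day 3) postdose for Cohort 1". For Cohort 2 it is "through a minimum of 120 hours postdose (Day 5) for Cohort 2". The Cohort 2 pair also appears in section 10.1 and twice in the Synopsis, under the summary of study design and under the dose escalation criteria.

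The Synopsis escalation entry and section 12.4.1 each end with a sentence on leaving enough time for the review. For Cohort 2 that time is counted "between Day 5 of Cohort 2 and the dose of the next cohort", with no hours given.

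The calendar is fixed elsewhere. Section 12.1 puts the single dose on Day 1. In the section 6 flow chart footnotes, "Subjects will be confined to the CRU until the completion of 168-hour blood draw and EOT procedures", and "EOT is defined as when the subject is released from the CRU following completion of all assessments through Day 8". Section 10.1 adds that Cohort 2 has "a sentinel group of 2 subjects who will be dosed at least 48 hours before the remaining 4 subjects".

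The clarification letter of 25 February 2019 adds a 3.5-hour ECG on Day 1 for Cohorts 2 and 3 and leaves the escalation wording unchanged.

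**The concern.** The hours and the day in the Cohort 2 rule do not name the same time, and nothing in the protocol says which governs. The window was set longer for Cohort 2 than for Cohort 1, so its length is a chosen safety parameter. The background gives reason for care: section 8.2.2 reports that in patients exposure rose more than in proportion to dose, and section 8.1.1 describes a steep dose-response for moribundity and death in animals.

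A team scheduling by study day could close the Cohort 2 review 24 h before the stated hours minimum. Dosing Cohort 3 on that review would satisfy one label and breach the other, and neither the site nor an auditor could tell from the text alone whether it was a deviation.

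**Working it through.** **Inputs**
- Dose at hour 0 of Day 1 (sections 6 and 12.1).
- Cohort 1 cut: 48 h, Day 3. Cohort 2 cut: 120 h, Day 5 (section 12.4.1).
- Last draw at 168 h; discharge on Day 8 (section 6, footnotes n and d).
- Flow chart hours after Day 1, in order: 24, 36, 48, 72, 96, 120, 144, 168, over Days 2 to 8.
- PK time points: 21 (section 13.4, Table 2).
- Two sentinels dosed at least 48 h before the other four (section 10.1).
- Half-life about 24 h, preliminary, in healthy subjects (section 8.1.1); those studies used 160 mg (section 8.2.2).

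**Step 1: the calendar.** Day d starts at 24 × (d − 1) hours.

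| Day | Starts at | Protocol text |
|---|---|---|
| 3 | 24 × 2 = 48 h | 48 h, Day 3: agrees |
| 5 | 24 × 4 = 96 h | paired with 120 h: disagrees |
| 6 | 24 × 5 = 120 h | not used in the rule |
| 8 | 24 × 7 = 168 h | 168 h, Day 8: agrees |

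**Step 2: check on the flow chart.** Reading its header this way gives 13 PK samples on Day 1 (predose to 12 h), 2 on Day 2 (24 and 36 h) and 1 on each of Days 3 to 8: 13 + 2 + 6 = 21, which matches Table 2.

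**Step 3: other conventions.**
- Dosing day as Day 0: 120/24 = 5 gives Day 5, but 48/24 = 2 and 168/24 = 7 contradict the stated Day 3 and Day 8.
- Each cut taken at the end of its named day: Day 5 ends at 24 × 5 = 120 h, but Day 3 then ends at 24 × 3 = 72 h, not the stated 48 h.

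Neither rule, applied to both cohorts, yields both pairs.

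**Step 4: size of the gap.** 120 − 96 = 24 h, and 24/120 = 20% of the stated minimum.

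**Step 5: who would be short.** When the last four subjects reach 96 h, the sentinels are at 96 + 48 = 144 h or later, already past 120 h. So at most 6 − 2 = 4 subjects lack the extra day.

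**Step 6: what would be missing at the decision.** Vital signs are taken once each study day (section 13.2.2), so one set, plus 24 h of adverse-event observation. The later scheduled ECGs are on Days 2 and 5 and at discharge (section 13.2.3). The Day 5 ECG is available under either cut, and none is named for Day 6.

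**Step 7: context.** With a 24 h half-life and simple exponential decline, 0.5^(96/24) = 6.25% of drug remains at 96 h and 0.5^(120/24) = 3.1% at 120 h. The next dose is at most 720/640 = 1.125 times a full Cohort 2 dose, a 12.5% step, and more if Cohort 2 is dosed below 640 mg.

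**The case against.** The best defence is that the hours are the operative rule and the day is a parenthetical label. A review closed at 96 h breaches the stated minimum, while waiting to 120 h satisfies both labels, so compliant conduct is available without any change. The two day-only sentences set no data cut; they add review time before the next dose and stand in the same entries as the 120 h minimum. Escalation also needs a positive judgement by the PI and the Sponsor. Nothing is lost to the trial, because subjects stay in the unit to 168 h. No objective, endpoint or analysis changes.

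Most of this stands and limits the consequence. In particular, the day-only sentences do not by themselves authorise a 96 h close. The residual-drug figures should carry little weight either way: they apply a preliminary half-life from 160 mg to doses up to 640 mg, although apparent clearance fell with dose in patients.

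It can also be argued that the labels are compatible, with 48 h opening Day 3 and 120 h closing Day 5. That reads one cut at the start of its day and the other at the end of its day within a single sentence, and the flow chart still places the 120 h visit on Day 6. It does not remove the contradiction.

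**Conclusion.** The rule is wrong as written: it gives the Cohort 2 minimum two values, 96 h by day and 120 h by hours. The error is repeated consistently and is not corrected by the clarification letter.

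The practical size is small: 24 h of observation for at most four subjects, before an optional cohort. A 96 h close is a possible reading, not a necessary one, and escalation would not be automatic at that point. The correction is still worth making, because the sentence states a safety threshold.

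The result assumes that study days run in 24 h steps from the dose, which the 48 h and 168 h anchors and the count of 21 samples support. The estimate of what would be missing assumes that no laboratory panel is scheduled between 96 h and 120 h; this should be checked against the laboratory row of the flow chart. The protocol does not show which cut was intended. The Day 5 ECG is a hint towards 96 h, but no more than that.

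**What to change.** Write *120 hours postdose (Day 6)* in the four paired places: the Synopsis summary of study design, the Synopsis escalation criteria, section 10.1 and section 12.4.1. Change Day 5 to Day 6 for Cohort 2 in the closing sentence of the Synopsis escalation entry and of section 12.4.1. This keeps the stated hours and is the safer reading.

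If 96 h was intended, write *96 hours postdose (Day 5)* in the four paired places and leave the two day-only sentences as they are.

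The first option costs a wording correction in six places and at most one calendar day before the optional Cohort 3.
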